**18 Data collection methods**

**18a Plans for assessment and collection of outcome, baseline, and other trial data**

Baseline data will be collected at the first appointment in the outpatient clinic or online via link in an email after the oral information has taken place. The Informed consent is filled out in Redcap before baseline information. During the intervention the participants will be followed closely and monitored on progression of tendon healing and adverse events. Assessment of outcome takes place at 9, 13, 26 and 52 weeks and will include patient reported questionnaires and physical measurements. Participant data will be stored in REDCap hosted at Aalborg University Hospital.

The personnel providing the randomization, exercise interventions and follow-up will follow standardized protocols for the intervention and receive training before initiation of the study. During the study there will be quality control regarding adherence to the protocols.

**18b Plans to promote participant retention and complete follow-up**

During the first visits, the participants are informed about the importance of adherence to the exercise intervention. They will follow the usual plan for clinical follow-up in the outpatient clinic,

where the staff can assist in solving any problems with attaining the study follow-ups. In case of adverse events or deviation from the treatment plan, the follow-up sessions will be executed if possible. For example, if physical examinations are not possible due to re-rupture, then only the patient questionnaires will be completed.

## **19. Data management**

All data will be stored electronically and are handled according to the General Data Protection Regulation. Participant data will be stored in REDCap hosted at Aalborg University Hospital. It is a secure web application for building and managing online surveys and databases and has secure logged entry. Data processor agreements and protocols will be stored on a secure server at Aalborg University Hospital. Any paper forms will be kept in a locked room in the outpatient clinics at the study sites. To prevent data entry errors, data collection instruments have been developed in REDCap so that required data must be included or an error will be displayed, and validation of each field has been chosen (e.g. if the format of the data does not appear to be a date in the field 'Date', an error is displayed). All data will be kept for 10 years after completion of the trial in accordance with The European Code of Conduct for Research Integrity.

## **20. Statistical methods**

### **20a Statistical methods for analysing primary and secondary outcomes**

The primary intention-to-treat analysis will investigate the between-group difference in ATRS. We will use a linear mixed effects regression model with the participant as random effect and time 13, 26 and 52 weeks, group allocation (standard care vs standard care plus add-on) and baseline value as fixed effects. Conclusions will only be drawn based on the primary endpoint (13 weeks).

All statistical analyses will be performed by a blinded data analyst according to a pre-established analysis plan. This plan is written in consultation with a statistician and will be published on the Aalborg University website before the inclusion of the last participant. STATA will be used as statistical software. We will use Q-Q plots and histograms to assess data normality.

### **20b. Methods for any additional analyses (eg, subgroup and adjusted analyses)**

N/A

### **20c Definition of analysis population relating to protocol non-adherence (eg, as randomised analysis), and any statistical methods to handle missing data (eg, multiple imputation)**

The intention-to-treat principle is used for analyses and all participants are included in the analyses regardless of the compliance to the intervention.

#### 21b Description of any interim analyses and stopping guidelines

If the rate of re-rupture or other serious adverse events is noted to be exceptionally high or increases rapidly after the intervention has been implemented, the DMC can recommend terminating the trial.

### 22. Harms

All participants receive information about possible adverse events relative to the Achilles tendon rupture in general and to the specific intervention. In case of serious adverse events they are encouraged to seek immediate medical attention and for minor adverse events to contact the project physiotherapist by phone. At each session the participants will answer questions of possible adverse events during and between the sessions. During and after completion of the study the included participants will also be followed in the outpatient clinic and in The Danish Achilles tendon Database (DADB).

### 23. Auditing

N/A

## Ethics and Dissemination

### 24. Research ethics approval

Before initiation of the study, approval of the study protocol, informed consent and participant information will be approved by:

- The Physiotherapy and Occupational therapy department and the Orthopaedic Department at Aalborg University Hospital
- The Ethics committee of North Denmark Region. Project identification number: N-20200041

As this is designed as an add-on intervention to standard of care, all participants will receive an evidence-based treatment that is at least equal to standard care today.

### 25. Protocol amendments.

Important protocol modifications are registered and approved by The Ethics committee of North Denmark Region.

### 26ab. Consent or assent

The primary investigator will obtain informed consent from the participants.

### 27. Confidentiality

All personal data collected on potential and enrolled participants is collected by telephone screening, at baseline appointment or at study sessions. Data will be kept secure and for 10 years. The GDPR – General Data Protection Regulation is followed. The study is registered at The Danish Data Protection Agency at Aalborg University Hospital.

### 28. Declaration of interests

All authors have no competing interests.

### 29. Access to data

All authors will have access to the full dataset before publication. The dataset will be stored at the sponsor site, Aalborg University hospital.

### **31a. Dissemination policy**

The results of the study will be submitted for publication regardless of the result being positive, negative or inconclusive. Publication will be aimed at an international peer-reviewed journal. The preliminary title is: “A randomised controlled trial on the effect of Early progressive strength exercise for treatment of acute Achilles tendon rupture. The Achilles tendon Back-On-Track study”. The results will also be presented at relevant physiotherapy and orthopaedic conferences. Guidelines and the exercise protocol will be made available for online download, to ensure translation of the research results into useful information for clinical practice.

### **31c. Plans, if any, for granting public access to the full protocol, participant-level dataset, and statistical code**

Data will be available upon reasonable request.

## [Appendices](#)

### **32. Informed consent materials**

### **33. Biological specimens**

None

**RCT study. Schedule of exercise program.**

Exercises					Elastic 1	Heelrise	Heelrise	Elastic 2	Elastic 2	Elastic 2					
					Heelrise	Heelrise	Heelrise	Heelrise	Heelrise	Heelrise					
					Iso	Iso	Iso	Elastic 1	Elastic 1	Elastic 1					
					Iso	ROM	ROM	ROM	ROM	ROM					
Weeks	1	2	3	4	5	6	7	8	9						
Immobilizing	Walker, 3 wedges			Walker, 2 wedges		Walker, 1 wedge		Walker, no wedge							
Weight bearing	Non WB		P- WB, 2 crutches		P-WB, 1-2 crutches		Full WB, crutches for long walk								
Rationale		A. Facilitation		B. Initiation of load			C. Progression to more load								
Total exercise dose (time under tension)		Facilitation of muscle activity by isometric contraction without ROM		Slow controlled movement to avoid peak forces on tendon while prioritizing long TUT to maintain/increase strength			Improve strength (go to failure IF THEY ARE comfortable with it)								
Progression		Progress from A to B: If patient feel comfortable doing facilitating exercises If clinical screening is OK at "2-week follow-up" (no tendon gap, equal ATRS, no pain during exercises).		Progress from B to C: If patient feel comfortable doing "initiation of load" exercises. If exercises are managed well - with regards to Toigo descriptors, - without persistent pain or discomfort during and after exercises, - no compensating movements while performing exercises.			Progress from C to exercise and mobilize without walker boot: The decision to discontinue the walkerboot is done at the Outpatient clinic. The exercises should provide the foundation for the patient to be confident in future decisions of choosing sufficient amount of load to improve the muscle performance while still avoiding too much strain on the healing tendon (i.e. avoid strenuous load, avoid stretching in dorsiflexion with load)								

Blue: Standard exercise program. Orange: Add-on exercises. Iso: Isometric contractions. Elastic 1: Light load (yellow-red). Elastic 2: Progression of load to stronger elastic band (red, blue, green). WB: Weight bearing. P-WB: Partial weight bearing. Heelrise is seated. ROM is unloaded range of movement.

Exercise descriptors table\_ClinicalTrials

**Appendix**

Toigo & Boutellier exercise descriptors	Isometric contraction	Seated heel-rise	Elastic band
X1 Load magnitude	15-20 RM	15-20 RM Progress to 15RM week 6/7	15-20 RM Progress to 15RM week 6/7
X2 number of repetitions	5	10-15	10-15
X3 number of sets	5	3	3
X4 rest btw sets	5 sec	10 sec	10 sec
X5 number of exercise interventions	Every hour (approx 12 hours per day) for week 2-3, then change to 5 times per day in week 4-9	5 per day	5 per day
X6 duration of the experimental period	Week 2 to 9	Week 3 to 9	From week 5 to 9
X7 Fractional and temporal distribution of the contraction modes per repetition and duration (s) of one repetition	5 sec	3s shortening 3s isometric 3s lengthening	3s-3s-3s (Focus is on the concentric phase. Important not to push beyond the neutral position in the eccentric phase)
X8 Rest in-between repetitions	2	2	2
X9 Time under tension	125s per session 1625s per day (hourly)  625s per day (5 times)	270-405s per session 1350-2025s per day	270-405s per session 1350-2025s per day
X10 Volitional muscular failure	No	No	No
X11 Range of motion	No range of motion. The foot is immobilized in equinus according to the number of wedges.	From plantarflexed foot position on the wedges to more plantarflexed, when performing the heel-rise	Dorsiflexion above neutral is not allowed. Full plantarflexion allowed.
X12 Recovery time in-between exercise sessions	1 hour	3 hours	3 hours

Exercise descriptors table\_ClinicalTrials

X13 Anatomical definition of the exercise (exercise form)	
Isometric contraction is performed inside the walkerboot with the foot in equinus according to the week-plan.
 
Push the forefoot against the bottom of the walker and feel the contraction of the leg muscles as if you are going to make a heel-rise, but the walker boot restricts your motions. Extend the big toe to minimize the activity of the muscles for the big toe and increase activity of the leg muscles.
 
From week 6 the exercise can be performed in standing.
	
Seated heel-rise with leg in walker with "the wedges of the week". Open straps and liner of walker. Knee in 90 degrees position. Hold one hand at the back of the walker to stabilize.
 
Lift the heel from the walker/wedges. Make sure that you are using the leg muscles and not pulling up the leg with your thigh muscles.
 
Extend the big toe to minimize the activity of the muscles for the big toe and increase activity of the leg muscles. Rest the foot on the forefoot pad rather than on the toes alone.
 
Progression: add weight on knee (either water bottle, upper body, weights - sandbag/kettlebell)
	
Performed seated with straight knee. Wrap the elastic band around the forefoot and hold both ends in the hand. Tighten the band, but make sure that the foot is not pulled beyond 90 degrees.
 
Press the foot down against the tightened elastic band as far as you can move the foot. Hold the position and then slowly pull up the foot again, but still with a tightened band.
 
Progression: Tighten the band or change the band to other color (more strength)

Level of load	
Borgs scale – Perceived exertion during exercise (/10) is used to guide the patients to progress or regress the load in each exercise. The recommended level being "easy" to "hard" (2-5/10). It is emphasized that the exercises must not cause sudden or severe pain in the tendon, but muscle soreness is to be expected.
		
Progression	
Progression of the exercises will be a continuous process. There are three main phases: facilitating, initiation of load, progression to more load. When progressing to the next phase or new type of exercise the following criteria must be observed:
 
The load magnitude of the present exercise should be accomplished with the patient feeling comfortable doing the exercises and without persistent pain or discomfort during and after exercises.

## 1. Study Synopsis

Regardless of choice of either surgical or non-surgical treatment for Achilles tendon ruptures, there is known long-term muscular deficits and a decreased function after Achilles tendon rupture(1,2). Early functional rehabilitation (EFR) during the first eight weeks of treatment is a multimodal strategy with elements ranging from weight-bearing to more specific exercises intended to load the Achilles tendon. Generally, the design of the intervention protocols in the available literature are very heterogeneous and the contents of EFR varies considerably(3,4), and few studies has examined the effect of strengthening exercises(5–7). We performed a feasibility study where early progressive resistance exercises showed high acceptability by the patients and the compliance with the exercises were high. The aim of this study is to investigate the efficacy of standard care versus standard care combined with early progressive resistance exercises in improving the Achilles tendon Total Rupture Score (ATRS) 13 weeks after non-surgical treated Achilles tendon rupture.

## 2. Study Objectives, Hypothesis and Outcomes

### 2.1. Primary Objective and Outcome

The primary objective is to investigate the efficacy of standard care versus standard care combined with an early exercise program in improving the ATRS (8,9) 13 weeks after non-surgical treated Achilles tendon rupture.

We hypothesize that individuals with Achilles Tendon rupture randomized to standard care with early exercises will have a significantly higher ATRS score after 13 weeks (primary endpoint) compared to individuals receiving standard care only.

The primary outcome ATRS is a validated self-reported questionnaire for acute Achilles tendon rupture. It consists of 10 items concerning limitations related to symptoms and physical function. Each item is rated from 0 (very limited function) to 10 (not at all limited). Items: strength, fatigue, stiffness, pain, activities of daily living, walking on uneven surfaces, walking quickly upstairs or uphill, running, jumping and hard physical labour. The ATRS is validated in a Danish population(9) and is used in the Danish Achilles Database DADB(10).

### 2.2. Secondary Objectives and Outcomes

The secondary objectives are to compare the secondary outcomes between standard care versus standard care combined with an early exercise program. In long-term follow-up to compare changes from 13 weeks follow-up to 26 and 52-weeks follow-up between groups. The objective outcomes are measured for injured and un-injured side and also presented as a side to side difference.

The outcomes are:

1. ATRS at 26- and 52 weeks

2. Physical Activity Questionnaire (IPAQ)(11) short form Danish version. It consists of 7 items concerning physical activity and gives an estimate of the total weekly physical activity measured in MET-minutes per week. The questionnaire will be filled out at 13-, 26- and 52-weeks follow-up.
3. Fear of re-rupture is measured by The Tampa scale of Kinesiophobia (TSK) (12). The questionnaire consists of 17 items concerning pain and kinesiophobia and has 4 answers from “Strongly disagree” to “Strongly agree” with a total range of 17 to 68 points. Four questions are reversed. Measured at baseline and at 9-, 13- and 52-weeks.
4. Fear of loading the Achilles tendon. Dichotomous Yes/no
  - a. During exercises. Measured at 9-weeks.
  - b. After weaning of the walking boot. Measured at 13 weeks
5. Percentage of the patients that can perform a one-legged heel-rise at 13- and 52 weeks.
6. Muscle endurance is measured with the MuscleLab measurement system (Ergotest Technology, Oslo, Norway)(13). Presented in Joules and repetitions.
  - a. Seated heel-rise test at 13 weeks\*. External weight load on the knee is calculated to 30% of the bodyweight.
  - b. One-legged standing heel-rise test at 52-weeks.
7. One-legged heel-rise height(13). Presented in centimeters.
8. Isometric muscle strength. Measured as maximal isometric plantar flexor muscle strength using Fysiometer(14). Position: seated with 90 degrees flexion in hip and knee. Measured at 9, 13, 52 weeks.
9. Achilles tendon resting angle (ATRA) is validated as an indirect measure of the Achilles tendon length (15).
10. Achilles tendon length in centimeters. Copenhagen Achilles length measure (CALM) using ultrasound(16). Performed at 9, 13 weeks and 52weeks.
11. Serious adverse events: Re-rupture, non-union, deep vein thrombosis (DVT).
12. Compliance with exercises. Number of sessions.
13. Cost-effectiveness outcomes. Self-reported health state as measured by the EQ-5D-5L(17). Work productivity outcomes are measured using the Work Productivity and Activity Impairment Questionnaire WPAI:GH (18) and condition-related expenses as measured by a self-developed questionnaire. Measured at 9, 13, 26, 52 weeks.

\* Measures of strength endurance is different at the shortterm follow-up 13-weeks and 52-weeks as the standing one-legged heel-rise is not possible to perform for all patients in the early phase(13).

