Several studies have reported use of controlled ankle/foot exercises, but few studies examined the effect of the exercises on its own and even fewer combined with non-surgical treatment.(22-25) We conducted a systematic review investigating the EFR used in the first 8 weeks of treatment and it showed very heterogeneous intervention protocols.(26) The components used in the EFR ranged from early weight-bearing and controlled range of motion ankle/foot exercises to strength exercises. The resistance exercises used in the early phase were most often isometrics, seated heel-rises or resistance exercises with an elastic band, but many studies did not describe the exercises and lacked information of exercise descriptors (eg. load, repetitions, sets) needed for a replication.(27)

Based on the results from this systematic review and our clinical expertise we designed a new, well-defined treatment protocol with exercises that were initiated earlier and with more progression than standard care today. We recently tested the feasibility of this new treatment protocol (N-20180072) which showed that the early initiation of exercises was highly feasible and patient acceptability was high. Based on our findings from 1) the systematic review and 2) our recently completed feasibility study, we now wish to test and compare this intervention to the current standard care that is delivered today. Such an intervention has the potential to negate the negative long-term functional consequences of Achilles tendon ruptures. By enhancing the physical function in the early stage, patients will have less sick leave and be able to return to work earlier. We expect that restoring early function could also positively benefit long-term outcome.

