## **7. Objectives**

The purpose of this trial is to investigate the efficacy of standard care versus standard care combined with an early exercise program in improving the Achilles tendon Total Rupture Score ATRS(28) score 13 weeks after non-surgical treated Achilles tendon rupture.

We hypothesize that individuals with Achilles Tendon rupture randomized to standard care and early exercises will have a significantly higher ATRS score (primary outcome) after 13 weeks (primary endpoint) compared to individuals receiving standard care only.

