The Tampa scale of Kinesiophobia (TSK) is used and validated for backpain, but has previously been used for Achilles tendon rupture evaluation as the questions about kinesiophobia could have associations to how patients with Achilles tendon rupture manage rehabilitation and return to sports.(40) The questionnaire consists of 17 items concerning pain and kinesiophobia and has 4 answers from “Strongly disagree” to “Strongly agree”. Measured at baseline, 9, 13 and 52 weeks.

Question: Were you afraid to do the prescribed load when performing the exercises? If yes why?  
Measured at 9 weeks

**Compliance with the intervention:** The participants will register the number of exercise sessions they perform each day in a training journal. The timeframe will be from the day they start the exercises to the end of week 9.

**Safety and Adverse events.** The number of serious and minor adverse events is registered in a pre-defined list based on Common Terminology Criteria for Adverse Events(43) and the participants will be asked open questions at each session. Serious adverse events are re-rupture, non-union of the tendon or symptomatic deep vein thrombosis (DVT). Muscle soreness or mild pain is considered inevitable and normal when initiating exercises after a period of immobilization.

**Cost-effectiveness outcomes.** To evaluate the cost-effectiveness of the intervention, we will use self-reported health state as measured by the EQ-5D-5L.(44) Work productivity outcomes are measured using the Work Productivity and Activity Impairment Questionnaire WPAI:GH and condition-related expenses as measured by a self-developed questionnaire. The EQ-5D provides a simple descriptive profile and a single index value for health status and has been used extensively in research to measure QALYs gained and thereby perform health economic evaluations. The questionnaires will be filled out during all follow-ups.

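### SAP 2.2 sets the long-term comparison as change from week 13, itself an outcome visit, so a benefit that is fully kept shows as zero and control catch-up shows as a negative difference

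*SAP*

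**What the plan says.** SAP 2.2 opens with a general aim: "The secondary objectives are to compare the secondary outcomes between standard care versus standard care combined with an early exercise program". The next sentence turns to the later visits: "In long-term follow-up to compare changes from 13 weeks follow-up to 26 and 52-weeks follow-up between groups". The first outcome then listed is "ATRS at 26- and 52 weeks", which is a value at each visit and not a change. Nothing in the section says which of the two is the long-term result.

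On the status of week 13, SAP 2.1 predicts that the intervention arm "will have a significantly higher ATRS score after 13 weeks (primary endpoint) compared to individuals receiving standard care only". Protocol 12 describes the window for recording exercise sessions: "The timeframe will be from the day they start the exercises to the end of week 9". The appendix of exercise descriptors also ends every exercise at week 9.

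On the long-term expectation, Protocol 6a says: "We expect that restoring early function could also positively benefit long-term outcome".

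On comparability over time, the footnote to SAP 2.2 says: "Measures of strength endurance is different at the shortterm follow-up 13-weeks and 52-weeks". Protocol 9 places physical follow-up at weeks 9, 13 and 52 only.

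On analysis, SAP 6.1 fits a mixed model to ATRS at weeks 13, 26 and 52 with time, group and baseline value as fixed effects. It names no group-by-time term and limits conclusions to week 13. SAP 6.2 presents the secondary endpoints descriptively.

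**The concern.** A change score is a fair basis for comparing randomised arms when its reference was measured before treatment could act, because the arms then have the same expected reference value. Week 13 does not meet that condition. It follows the randomised exercises by four weeks, and the trial's hypothesis is that the arms differ there. Subtracting the week-13 value removes from the long-term estimate the very effect the trial sets out to show.

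The stated contrast can be positive only if the advantage grows after week 13. A lasting benefit, which is what Protocol 6a hopes for, would read as no difference. A benefit that controls later match would read as a deficit, although the intervention arm was never behind. Some narrowing is plausible: ATRS has a ceiling of 100 (10 items, each 0 to 10), and Protocol 11a refers both arms to the same group rehabilitation from week 9 to week 17.

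At stake is how the 26- and 52-week results are read. Depending on which sentence of SAP 2.2 an analyst follows, the long-term estimate can differ in size and even in sign.

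**Working it through.** **Inputs from the documents.** Effect at week 13: 10 points; SD 15; two-sided 5%; 80% power; 37 per arm, 82 in total (SAP 3.1). Exercises end at week 9 (Protocol 12 and appendix).

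**Assumptions, not in the documents.** SD of 15 at week 52 as well; correlation r between week-13 and week-52 ATRS of 0.3, 0.5 or 0.7. The week-52 differences below are scenarios, not forecasts.

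**The plan's own figure.** n per arm = 2 × (1.96 + 0.84)² × 15² / 10² = 35.3, so 36 by the normal approximation. The two-sample t-test gives 36.3, so 37, with 80.8% power. The stated 37 is reproduced and is not in dispute.

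**What the contrast estimates.** Let D13 and D52 be the intervention-minus-control differences in mean at weeks 13 and 52. Then:

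(T52 − T13) − (C52 − C13) = (T52 − C52) − (T13 − C13) = D52 − D13

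| Scenario | D13 | D52 (difference in value) | D52 − D13 (difference in change) |
|---|---|---|---|
| Benefit grows | 10 | +15 | +5 |
| Fully kept | 10 | +10 | 0 |
| Half kept | 10 | +5 | −5 |
| Full catch-up by controls | 10 | 0 | −10 |
| No effect at either visit | 0 | 0 | 0 |

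The two contrasts agree in expectation only when there is no effect at week 13. The same algebra holds at week 26. For scales where lower is better, such as the TSK, the signs reverse.

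**Precision.** SD of change = 15 × √(2(1 − r)); SE = SD of change × √(2/37).

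| r | SD of change | SE | 95% half-width (1.96 × SE) |
|---|---|---|---|
| 0.3 | 17.75 | 4.13 | 8.1 |
| 0.5 | 15.00 | 3.49 | 6.8 |
| 0.7 | 11.62 | 2.70 | 5.3 |

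For a difference in value, SE = 15 × √(2/37) = 3.49. An estimated −10 in the change contrast would have a 95% interval wholly below zero at all three correlations.

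**If the contrast were tested**, which the SAP does not plan, the chance of a nominally significant negative result for r = 0.3, 0.5 and 0.7 would be 0.68, 0.82 and 0.96 under full catch-up, and 0.23, 0.30 and 0.46 with the benefit half kept. A fully kept 10-point benefit would come out significantly positive 2.5% of the time on change, against about 82% on the week-52 value.

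**Where the change cannot be formed.**
- Muscle endurance: a seated test with a knee load at week 13, a one-legged standing test at week 52.
- Any physical measure at week 26: no physical visit.
- TSK at week 26: collected at baseline and weeks 9, 13 and 52 only.
- The two fear-of-loading questions: each asked once (week 9 and week 13).

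**The case against.** The strongest reply is that the SAP does not commit itself to this contrast alone. The sentence just before it sets a general between-group comparison, later ATRS is listed by visit, and SAP 6.1 models values adjusted for the recalled pre-rupture score, not changes from week 13. On that reading the sentence adds a look at trajectory. This stands in part: a reader might infer that change from week 13 is the only long-term comparison, and the text does not say so. But it does not give the level comparison priority either, and the sentence in question is the only one that says how the later visits are to be compared.

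A reader might also infer that the trial could formally conclude against its own intervention. The documents do not support that. Both restrict conclusions to week 13, and SAP 6.2 makes the secondary endpoints descriptive. The significance probabilities above therefore describe an unplanned test. A descriptive table of changes by arm would still show 0 or −10, because the problem lies in the quantity estimated and not in the test.

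Third, −10 under full catch-up is a correct number: controls did gain 10 points more after week 13, and the primary result printed beside it would let a careful reader see why. That is fair. Calling the figure harm would be a misreading, and whether controls catch up is a legitimate descriptive question. It is not the question whether treated patients are better off at one year.

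Finally, the SAP footnote already discloses that the endurance tests differ. It does not exempt endurance from the change comparison.

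**Conclusion.** The point holds as a defect in a stated secondary objective. The long-term contrast in SAP 2.2 uses a post-treatment visit as its reference and so estimates the later difference minus the week-13 difference. With the SAP's 10-point effect at week 13, it understates the week-52 difference in ATRS by 10 points whatever happens afterwards: 0 in place of +10, −5 in place of +5, −10 in place of 0. That result is algebra and needs only a 10-point difference at week 13. The standard errors also rest on the assumed correlation and on an SD of 15 at week 52.

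The consequence is a misleading secondary estimate. It is neither a threat to the primary analysis nor a route to a false formal conclusion. For muscle endurance, and for physical measures at week 26, the comparison as worded cannot be carried out. This is a cheap improvement.

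**What to change.** In SAP 2.2, replace the sentence on change from week 13 with wording to this effect: the long-term between-group estimate is the difference in value at 26 and at 52 weeks, adjusted for the pre-injury baseline where collected. Then:

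- **SAP 6.1:** add a group-by-time term so that the existing mixed model yields a group difference for ATRS at each visit. With a single group term it gives one common difference across visits.
- **SAP 6.2:** state that these later differences are reported with confidence intervals. Changing 2.2 alone would leave it at odds with a purely descriptive 6.2.
- **Physical outcomes:** state that their long-term comparison is at week 52. The comparisons planned at weeks 9 and 13 stay as they are.
- **Change from week 13:** keep it only as a description of recovery within each arm, and not for muscle endurance, where the test differs.

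The cost is SAP wording and one model term. No new visit, test or participant is needed, and conclusions can still rest on week 13. The downside is that between-group recovery rates after week 13 are no longer a stated comparison; neither document has a hypothesis that depends on them.
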